6.1.6 Duration of Therapy

Treatment with study drug continues until disease progression, unacceptable toxicity (AE related to study drug), or the subject meets other criteria for discontinuation of study drug outlined in [Section 5.3](#).

The Sponsor will ensure that subjects who are benefiting from study treatment can continue to receive study treatment after the CCO for the final OS analysis. For these subjects, study treatment will be available through continued access within the current study until it is available through another source such as commercial availability with reimbursement, continued access through a long-term extension study, a patient access program, or after the last subject transitions into the long-term extension phase of the study up to 30 September 2024, whichever occurs first.

The long-term extension phase of this study will begin at the time of the CCO for the final OS analysis and is intended to provide ongoing access to study treatment for subjects who continue to benefit from such treatment. Certain long-term safety data will continue to be reported for these subjects, as described in [Appendix 12](#).

No eCRF data will be collected after the CCO date for the final OS analysis (when approximately 166 deaths have been reported). All eCRF data collected up to this timepoint will be included in the final study analysis and reported in a separate clinical study report.

The investigational sites are requested to notify the Sponsor within 1 working day if a subject has been diagnosed with disease progression (that is also confirmed with a consecutive assessment if based on M-protein/serum FLC levels) and provide documentation of disease progression. The Sponsor's medical monitor will review the data provided to confirm that the IMWG criteria for PD have been met, refer to [Section 7.1.1](#) (Sponsor Confirmation of Progressive Disease). For subjects continuing the study after the positive primary analysis, notification of PD and approval by the Sponsor is no longer required. Please refer to [Section 7.1.1](#) (Sponsor Confirmation of Progressive Disease) for updated procedures.

6.2 STUDY TREATMENT ACCOUNTABILITY PROCEDURES

The investigator, or a pharmacist or other appropriate individual who is designated by the investigator, will maintain accurate records of the product's delivery to the study site, the inventory at the site, the use by each subject, and the return to the Sponsor or alternative disposition of unused product(s). Monitoring of drug accountability will be performed by the field monitor during the study conduct and a copy of the final drug accountability and reconciliation log will be provided by the investigator(s) at the completion of the study.

Daratumumab will be administered by qualified staff and the details of each administration will be recorded in the electronic case report form (eCRF).

A diary will be used to assess compliance with the administration of pomalidomide and dexamethasone.

7 STUDY PROCEDURES AND SCHEDULE

Refer to [Appendix 12](#) for guidance regarding protocol-required procedures/evaluations for subjects continuing on study treatment after CCO for the final OS analysis.

7.1 STUDY PROCEDURES/EVALUATIONS

7.1.1 Efficacy Assessments

The primary endpoint of this study is PFS. Secondary efficacy endpoints are OS, ORR, DoR, and time to next therapy.

Response or disease progression will be assessed by the investigator for treatment decision based on the analysis of serum and urine protein electrophoresis (SPEP and UPEP), serum and urine immunofixation (sIFE and uIFE), serum free light chain protein (sFLC), imaging and bone marrow assessments, per modified IMWG guidelines ([Appendix 2](#)). The statistical analysis will use derived response or disease progression based on a validated computer algorithm that has been shown to provide consistent review of the data necessary to determine disease progression and response according to the modified IMWG criteria.

All efficacy laboratory assessments will be collected locally and analyzed centrally unless otherwise indicated in [Table 7.1](#). The disease assessments SPEP, UPEP, and serum calcium corrected for albumin should be collected every cycle for the first 14 months of the study and every other month thereafter. After Cycle 1, IFE should only be done when endogenous M-protein is 0 or nonquantifiable. For subjects who are followed by FLC only, these assessments are performed every other cycle after 14 months. If the subject does not have documented disease progression as defined in [Appendix 2](#) at the time of study drug discontinuation, then disease assessments must continue to be performed according to the same schedule

shown in *Table 7.3* until disease progression even if a subsequent anti-myeloma treatment is started prior to disease progression:

- Laboratory analysis for response assessment (SPEP, UPEP, sIFE, uIFE, sFLC)
- Minimal Residual Disease analysis for subjects with suspected CR or better performed by next-generation sequencing according to *Table 7.1* and the Schedule of Events (*Table 7.3*)
- Daratumumab-specific Immunofixation Electrophoresis (DSIFE) for subjects with IgGκ sub-type achieving VGPR or better

The following assessments will be carried out at local laboratory, if available, or at the Erasmus laboratory:

- Cytogenetics by means of Fluorescence In Situ Hybridization (FISH) at study entry

Disease assessments will be collected locally and analyzed centrally unless otherwise indicated in *Table 7.1*.

Table 7.1: Disease assessment

M-protein by electrophoresis Serum ¹ (SPEP), Urine (UPEP)	Screening and baseline Day 1 of each required cycle End of treatment Post-treatment follow-up every 4 weeks As needed to confirm disease progression
M-protein by immunofixation Serum ¹ (sIFE), Urine (uIFE)	Screening and baseline Day 1 of each required cycle End of treatment Post-treatment follow-up every 4 weeks
Serum free light chain sFLC ¹	Screening and baseline Day 1 of each required cycle End of treatment Post-treatment follow-up every 4 weeks As needed to confirm disease progression for subjects with serum FLC only disease
DSIFE (see Section 7.1.1.3)	To confirm a VGPR or better in subjects with IgG kappa myeloma when daratumumab interference is suspected based on SPEP- and sIFE results
Clinical assessment of soft tissue plasmacytoma (STP) – to be done locally	Screening and baseline Day 1 of each cycle End of treatment Post-treatment follow-up every 4 weeks As needed to confirm disease progression
CT/MRI assessment of STP – to be done locally	At screening upon positive findings from clinical assessment and as clinically indicated. For subjects with plasmacytomas identified at screening, CT/MRI should be done every 3 cycles
Plasma cell count in bone marrow - to be done locally	At screening and during the study as clinically indicated to substantiate CR.
Skeletal survey by X-ray and/or CT/MRI – to be done locally	At screening and as clinically indicated, CT/MRI in case of newly symptomatic areas with no X-ray finding.

Corrected calcium ¹	Screening and baseline Day 1 of each cycle End of treatment Post-treatment follow-up every 4 weeks As needed to confirm disease progression
MRD by means Next-Generation Sequencing	To be performed at time of suspected CR/sCR and 6, 12, 18, 24, and every 12 months (yearly assessments \pm 3 months) post CR/sCR in subjects who maintain CR or sCR, until PD is observed.

¹ Disease assessments SPEP, UPEP, and serum calcium corrected for albumin, should be collected every cycle for the first 14 months of the study and every other month thereafter. After Cycle 1, IFE should only be done when endogenous M-protein is 0 or nonquantifiable. For subjects who are followed by FLC only, these assessments are performed every other cycle after 14 months.

Additional local laboratory tests will be collected in accordance with standard clinical practice and medicinal products' SmPCs

Confirmation of Response

Based on modified IMWG criteria, response must be confirmed for all categories other than SD in order to rule out errors. A consecutive assessment can be performed at any time and confirmation should be obtained by M-protein assessments.

- Bone marrow assessments do not need to be repeated, but at least 1 bone marrow assessment is required to substantiate a CR.
- If imaging studies were done, they need to rule out new lytic bone lesions.
- Should confirmation assessments reveal a better category (eg, VGPR after PR), the response category of the previous assessment will be considered as confirmed (PR).
- Should confirmation assessments reveal a worse category, (eg, VGPR after CR), the response category of the subsequent assessment will be considered as confirmed (VGPR).
- Should repeated measurements of a variable result in more values, the worst assessment is to be considered.

Laboratory Confirmation of Progressive Disease

A diagnosis of PD requires confirmation if determined based on M-protein measurement or serum FLC levels. Confirmation of an increase in M-protein or FLC should be obtained as soon as possible.

See [Section 7.1.1.3](#) for information concerning possible false protein electrophoresis (PEP) and immunofixation (IFE) results.

Sponsor Confirmation of Progressive Disease

A diagnosis of PD (that is also confirmed with a consecutive assessment if based on M-protein/serum FLC levels) must be reported, via email, to the Sponsor's Medical Reviewer within 1 working day using the Progressive Disease Notification Form together with all supporting documentation for the diagnosis. The Medical Reviewer will check that the investigator's assessment of PD is consistent with the IMWG criteria and will provide a confirmation on the same form and return it via email to the site. In the case that the investigator's assessment is not deemed consistent with the IMWG criteria, the Medical Reviewer will

provide comments in the relevant section of the notification form and may also contact the investigator to discuss the subject further.

Study treatment discontinuation and start of subsequent anti-myeloma therapy should occur only after Sponsor confirmation of PD.

For subjects continuing on the study after the positive primary analysis and final OS analysis, investigator assessment of PD should continue to be performed in accordance with IMWG criteria. Notification of PD and approval by the Sponsor is no longer required.

7.1.1.1 Serum and Urine Sample Collection for M-protein Assessment by PEP and IFE

Response to treatment is based on M-protein levels in serum and urine. Two methods are required:

- Protein electrophoresis provides quantitative measurements.
 - Immunofixation provides qualitative measurements (present/absent). It is a more sensitive method than PEP and is used to confirm the absence of M-protein by PEP (CR).
- Serum and urine IFE is required at baseline and to confirm CR regardless of whether measurable M-protein was present at baseline.
- Subjects with measurable disease in SPEP will be assessed for response based on SPEP and not by the serum FLC assay.
- Subjects with measurable disease in both SPEP and UPEP will be assessed for response based on these 2 tests and not by the serum FLC assay.

Blood (serum) and 24-h urine for M-protein assessment will be collected as indicated in [Table 7.3](#).

Analysis by IFE will be done for all subjects at screening and baseline and thereafter only in subjects at time points in case of disappearance of M-protein by PEP.

7.1.1.2 Free Light Chain (FLC) Protein Assessment

The serum FLC assay measures free kappa light chain (0.33-1.94 mg/dL) and free lambda light chain (0.57-2.63 mg/dL). The FLC ratio is defined as the kappa serum level divided by the lambda serum level. Lambda is the involved light chain if FLC ratio <0.26 . Kappa is the involved light chain if FLC ratio is > 1.65 .

The FLC ratio is considered normal if FLC ratio is within 0.26-1.65 and Abnormal if FLC ratio is <0.26 or >1.65 .

FLC serves to monitor disease status when serum M-protein or urine M-protein or both, assessed by PEP, is/are non-measurable (ie, serum M-protein <0.5 g/dL [5 g/L] or urine M-protein <200 mg [0.2 g] per 24 hours) and to identify sCR if CR criteria are met.

Blood (serum) for FLC assessment will be collected as indicated in [Table 7.3](#). FLC will be analyzed only when serum M-protein or urine M-protein or both assessed by PEP is/are non-measurable and to identify sCR.

7.1.1.3 Daratumumab-specific Immunofixation Electrophoresis (DSIFE)

Daratumumab may be detected on SPEP and sIFE assays used for monitoring disease monoclonal immunoglobulins (M-protein). This can lead to false positive SPEP and sIFE assay results for subjects with IgG kappa myeloma protein and affect assessments of responses based on modified IMWG criteria.

Therefore, a DSIFE will be performed when daratumumab interference is suspected based on SPEP and sIFE results. This reflex assay relies on the use of a daratumumab-specific murine anti-idiotype antibody that binds and shifts daratumumab's migration pattern during electrophoresis, thus distinguishing daratumumab from the endogenous myeloma M-protein ([McCudden et al 2015](#)). The DSIFE will be performed at a central laboratory to confirm a VGPR or better in subjects with IgG kappa myeloma when daratumumab interference is suspected based on SPEP- and sIFE results.

7.1.1.4 Bone Marrow by Local Assessment

A BM aspirate, a biopsy, or both should be performed for every subject at screening. A portion of screening BM aspirate (first or second pull preferred) is also required for MRD, FISH and Biomarker assessments (central assessments: see [Table 7.2](#) and [Sections 7.1.1.7, 7.1.1.9](#) and [7.1.2.7](#) for more details). As the procedure is invasive, post-baseline assessments should be performed for confirmation of CR/sCR or, if clinically indicated, at time of suspected disease progression or end of treatment.

Plasma Cell Count in Bone Marrow

A bone marrow (BM) aspirate/biopsy for plasma cell quantification will be collected at screening and as clinically indicated to qualify for CR (see [Table 7.3](#)) and the percentage of plasma cells will be determined by using cytological/histological examination. In the event a fresh screening biopsy/aspirate cannot be collected, use non-decalcified diagnostic tissue (ie, bone marrow aspirate, touch preparation, or clot selection) or formalin-fixed paraffin embedded [FFPE] block (clot selection only, no bone marrow biopsy) from a sample taken within 42 days from C1D1.

Clonal plasma cell will be determined by either flow cytometry or immunohistochemistry or immunofluorescence in order to qualify for sCR (when CR criteria are met and a normal serum FLC ratio is also observed). Either BM aspirate or biopsy can be used for this assessment, but the same method should be used throughout the study. Bone marrow aspirate is required for MRD and flow cytometry assessment.

Table 7.2: Bone Marrow Testing

	Local Testing	Central Testing
Screening	
 • Plasma cell count (morphology) • Cytogenetics by FISH (if possible to perform locally) 	
 • MRD (baseline) • Cytogenetics by FISH (if not possible to perform locally) • Biomarkers (baseline)
Suspected CR, sCR	
 • CR Confirmation: Plasma Cell Quantification (morphology) • sCR Confirmation: immunohistochemistry, immunofluorescence (requires kappa/lambda ratio from analysis of ≥ 100 cells) or 2- to 4-color flow cytometry. 	
 • MRD • Biomarkers
Maintained CR, sCR	Not applicable	
 • MRD: For subjects who maintain CR/sCR, an additional bone marrow aspirate will be obtained at 6, 12, 18, 24, and thereafter every 12 months (yearly assessments ± 3 months), until PD is observed
Disease Progression	Not applicable	
 • Biomarkers: If feasible, a bone marrow aspirate may be collected from subjects at disease progression to evaluate mechanisms of daratumumab resistance.

CR=complete response; FISH=fluorescence in situ hybridization; sCR=stringent complete response; MRD=minimal residual disease; PD=progressive disease

7.1.1.5 Assessment of Soft Tissue Plasmacytoma (STP)

Clinical Assessment by Investigator

The investigator should perform a clinical exam to assess the presence of STP at screening and baseline, on Day 1 of each cycle, at end of treatment, and during post-treatment follow-up.

If presence of a STP is suspected during the study, a computed tomography (CT) or MRI must be performed immediately to confirm and document the lesions' dimensions.

- CT/MRI
 - Screening: A CT/MRI will be performed at screening within 28 days prior to start of study treatment. Any imaging assessments already completed during the regular work-up of the subject within 42 days prior to start of treatment can be considered as the baseline assessment.
 - Post-baseline: Assessments should be performed using the same imaging technique used at baseline.
 - If STP is present at baseline, a CT/MRI should be performed every 12 weeks (+/ 7 days) until disappearance of STP or disease progression.
 - If STP is not present at baseline, but there is a suspicion of STP and/or disease progression (based on clinical exam or symptoms), a CT/MRI should be performed promptly to confirm suspicion.

Lesion size will be measured as the sum of the products of the longest diameter and longest perpendicular diameter for all measurable lesions.

All tumor measurements must be made in millimeters. Measurable disease are lesions that can be accurately measured in 2 dimensions and both diameters must be ≥ 20 mm when evaluated by standard CT scanning or ≥ 10 mm when evaluated by spiral CT scanning or MRI. At baseline, lesions of smaller dimensions will not be considered measurable and will not be followed for disease evaluation except for assessment of disease progression (when the lesion size increases and becomes measurable as per the above guidance).

7.1.1.6 *Skeletal Survey*

A skeletal survey is to be performed by conventional radiography for osteolytic disease within 28 days prior to randomization in all subjects. Results from the skeletal survey which have been performed as routine follow-up within 42 days before C1D1, may be used without these tests being repeated. The survey will be performed during the study if clinically indicated. Use of conventional or low-dose CT scan (ie, of the spine) or MRI is acceptable. If imaging is performed on treatment for assessment of progression, the same imaging technique as the one used at screening must be used. The number and location of skeletal lesions and whether they are lytic should be recorded on the eCRF. On-treatment survey, if clinically indicated, it should be recorded whether there is an increase in the number or size of lytic lesions (as described in [Appendix 2](#)).

7.1.1.7 *Minimal Residual Disease (MRD)*

Minimal Residual Disease assessment by next-generation sequencing (NGS) is an effective tool in the assessment of patients with MM ([Ladetto et al 2014](#)). Several studies have demonstrated that MRD status is correlated with PFS and OS ([Martinez-Lopez et al 2014](#); [Kumar et al 2016](#); [Munshi et al 2017](#)). MRD will be analyzed at a central laboratory when BM aspirate sample is obtained at screening to establish the baseline clone and at the time of suspected CR/sCR and 6, 12, 18, 24, and every 12 months (yearly assessments ± 3 months) post CR/sCR in subjects who maintain CR or sCR, until PD is observed.

Following the CCO for the final OS analysis, MRD testing will be performed according to the standard of care for subjects without disease progression (see [Appendix 12](#)).

If a fresh bone marrow aspirate cannot be collected at screening, use non-decalcified diagnostic tissue (ie, bone marrow aspirate, touch preparation, or clot selection) or FFPE block (clot selection only, no bone marrow biopsy) from a sample taken within 42 days from C1D1.

7.1.1.8 *Corrected Calcium*

Corrected calcium in serum for determination of hypercalcemia as part of response assessment will be evaluated at screening/baseline and on Day 1 of each cycle until disease progression using the following formula:

Corrected Calcium, mg/dL = $(0.8 \times [\text{normal Albumin, g/dL} - \text{Subject's Albumin, g/dL}] + \text{Serum Ca, mg/dL})$ ([Appendix 5](#)).

7.1.1.9 *Cytogenetics by Means Of Fluorescence In Situ Hybridization (FISH)*

A cytogenetic analysis of BM cells will be performed at screening through FISH at local laboratory, if available, or at the Erasmus laboratory for del17p, 1q amp, t(4;14), and t(14;16).

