Appendix 1: The International Staging System (ISS) For Multiple Myeloma

Stage	Criteria	Median Survival (Months)
Stage 1	Serum β 2-microglobulin <3.5 mg/L Serum albumin ≥ 3.5 g/dL	62
Stage 2	Not stage I or III (There are 2 categories for stage II) serum β 2-microglobulin <3.5 mg/L but serum albumin <3.5 g/dL OR β 2-microglobulin 3.5 to <5.5 mg/L irrespective of the serum albumin level	44
Stage 3	Serum β 2-microglobulin ≥ 5.5 mg/L	29

Appendix 2: Modified International Myeloma Working Group (IMWG) Uniform Response Criteria for Multiple Myeloma

Response	IMWG criteria
Stringent complete response (sCR)	CR as defined below plus normal FLC ratio and absence of clonal cells in bone marrow ¹ by immunohistochemistry or immunofluorescence. ²
Complete response (CR)	Negative immunofixation on serum and urine and disappearance of any soft tissue plasmacytomas and <5% plasma cells in bone marrow. ¹
Very good partial response (VGPR)	Serum and urine M-protein detectable by immunofixation but not on electrophoresis or $\geq 90\%$ reduction in serum M-protein plus urine M-protein level <100 mg/24 h
Partial response (PR)	$\geq 50\%$ reduction of serum M-protein and reduction in 24 hours urinary M-protein by $\geq 90\%$ or to <200 mg/24 h. If serum and urine M-protein are unmeasurable, ³ a $\geq 50\%$ decrease in the difference between involved and unininvolved FLC levels is required in place of the M-protein criteria. If serum and urine M-protein are not measurable, and serum free light assay is also not measurable, $\geq 50\%$ reduction in plasma cells is required in place of M-protein, provided baseline bone marrow plasma cell percentage was $\geq 30\%$. In addition to the above listed criteria, if present at baseline, a $\geq 50\%$ reduction in the size of soft tissue plasmacytomas is also required.
Minor (Minimal) Response (MR)	25-49% reduction of serum M-protein and reduction in 24-hour urine M-protein by 50-89%, which still exceeds 200 mg per 24 hours. In addition, if present at baseline, 25-49% reduction in the size of soft tissue plasmacytomas is also required. No increase in the size or number of lytic bone lesions (development of compression fracture does not exclude response).
No change/Stable disease	Not meeting criteria for CR, VGPR, PR, or progressive disease.

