Progressive disease (PD) ³	Any of the following: 
 • Increase of $\geq 25\%$ from lowest response value in any one or more of the following: 
 ◦ Serum M-component and/or (the absolute increase must be ≥ 0.5 g/dL)⁴ ◦ Urine M-component and/or (the absolute increase must be ≥ 200 mg/24 h) ◦ Only in patients without measurable serum and urine M-protein levels; the difference between involved and unininvolved FLC levels. The absolute increase must be >10 mg/dL ◦ Bone marrow plasma cell percentage; the absolute percentage must be $\geq 10\%$⁵ • Definite development of new bone lesions or soft tissue plasmacytomas or definite increase in the size of existing bone lesions or soft tissue plasmacytomas ($\geq 50\%$ increase from nadir in SPD⁷ of >1 lesion, or $\geq 50\%$ increase in the longest diameter of a previous lesion >1 cm in the short axis). • Development of hypercalcemia (corrected serum calcium >11.5 mg/dL or 2.87 mmol/L) that can be attributed solely to the plasma cell proliferative disorder

Response	IMWG criteria
Relapse	
Clinical relapse requires one or more of:
 
Direct indicators of increasing disease and/or end organ dysfunction (CRAB features).⁴ It is not used in calculation of time to progression or progression-free survival but is listed here as something that can be reported optionally or for use in clinical practice
 
• Development of new soft tissue plasmacytomas or bone lesions• Definite increase in the size of existing plasmacytomas or bone lesions. A definite increase is defined as a 50% (and at least 1 cm) increase as measured serially by the sum of the products of the cross-diameters of the measurable lesion• Hypercalcemia (>11.5 mg/dL) [2.87 mmol/L]• Decrease in hemoglobin of ≥ 2 g/dL [1.24 mmol/L]• Rise in serum creatinine by 2 mg/dL or more [177 μmol/L or more]
Relapse from CR ³ (To be used only if the end point studied is DFS) ⁶	
Any one or more of the following:
 
• Reappearance of serum or urine M-protein by immunofixation or electrophoresis• Development of $\geq 5\%$ plasma cells in the bone marrow⁵• Appearance of any other sign of progression (i.e., new plasmacytoma, lytic bone lesion, or hypercalcemia)

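### Section 7.1.1.5 drops small baseline plasmacytomas from response follow-up although Appendix 2 lets none remain at CR, and on standard CT its size limit also misses growth that Appendix 2 counts as progression

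*Combined protocol and SAP*

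**What the plan says.** Section 7.1.1.5 of the protocol makes three statements that bear on this point.

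- Size limit: "Measurable disease are lesions that can be accurately measured in 2 dimensions and both diameters must be" at least 20 mm on standard CT, or at least 10 mm on spiral CT or MRI. Lesions under the limit at baseline "will not be followed for disease evaluation except for assessment of disease progression (when the lesion size increases and becomes measurable" by that guidance).
- Size calculation: "Lesion size will be measured as the sum of the products of the longest diameter and longest perpendicular diameter for all measurable lesions".
- Imaging: where a plasmacytoma is present at baseline, "a CT/MRI should be performed every 12 weeks (+/ 7 days) until disappearance of STP or disease progression". No minimum size is attached.

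Appendix 2 (modified IMWG criteria) has its own rules. CR needs "Negative immunofixation on serum and urine and disappearance of any soft tissue plasmacytomas", together with under 5% plasma cells in the marrow, and gives no size limit. An existing plasmacytoma counts as progressive disease (PD) in two ways. One is a rise of at least 50% from nadir in the sum of products of perpendicular diameters (SPD) of more than one lesion. The other is at least a 50% "increase in the longest diameter of a previous lesion" whose short axis exceeded 1 cm. A definite new plasmacytoma is PD with no percentage condition.

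Sections 7.1.1 and 10.1 take the analysed response and progression status from a validated computer algorithm that applies the modified IMWG criteria. PFS is defined once (Section 10.4.2), and so is the CR-or-better rate (Section 10.4.3).

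**The concern.** The algorithm can apply Appendix 2 only to the lesion data it receives. Table 7.1 has plasmacytomas examined and imaged locally, the trial is open-label, and 7.1.1.5 is the text that tells sites what to evaluate. It does not point to Appendix 2, although the skeletal survey section that follows it does. A site that takes 7.1.1.5 literally scans a small baseline lesion but does not evaluate it for response. The Appendix 2 condition for CR then cannot be checked for that lesion.

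CR-or-better belongs to the family of secondary endpoints with Type I error control (Section 10.4.9). Progression is part of the primary endpoint. There the question is narrower: could a lesion that has grown enough under Appendix 2 be left out because it is still below the 7.1.1.5 limit?

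**Working it through.** The check is mainly a comparison of texts. All lesion sizes below are illustrations, not trial data.

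**1. The plan's own figures.** Section 10.5 gives HR 0.621, one-sided 0.025, 90% power, 188 events, 280 evaluable and 302 randomized. With 1:1 allocation, the Schoenfeld formula gives events = 4 × (1.960 + 1.282)² / (ln 0.621)² = 185.2, so 186; the Freedman formula gives 193. At 188 events the power is 0.904. Allowing for 7% early censoring, 140 / 0.93 = 150.5, so 151 per arm and 302 in total. The plan's figures reproduce, and none of them depends on the plasmacytoma rules.

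**2. CR.** Take a 15 mm lesion on standard CT that persists.

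- Appendix 2: it has not gone, so there is no CR.
- Imaging rule in 7.1.1.5: scan every 12 weeks until it has gone.
- Follow-up rule in 7.1.1.5: it is below 20 mm, so it is followed only for progression, and only once it is measurable.

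The scan is required, but the finding that matters for CR is not. The inconsistency lies between 7.1.1.5 and Appendix 2, and also between two sentences of 7.1.1.5.

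**3. PD, single lesion, standard CT.** A lesion grows from 15x12 mm to 23x15 mm.

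- Longest diameter: 23 / 15 − 1 = +53%. The earlier short axis was 12 mm, above 1 cm, so the Appendix 2 single-lesion rule is met.
- The new short axis is 15 mm, below 20 mm, so the lesion is still non-measurable and the progression exception in 7.1.1.5 does not apply.

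A borderline case behaves the same way: 15x12 to 22.5x14 mm is +50% in longest diameter with a new short axis of 14 mm.

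**4. PD, single lesion, spiral CT or MRI.** A lesion with short axis above 1 cm has both diameters of at least 10 mm. It is therefore measurable from baseline, and the mismatch in step 3 does not arise. A small gap in coverage remains: 6x6 to 10x10 mm is 10 / 6 − 1 = +67% and becomes measurable, but the earlier short axis was not above 1 cm, so the Appendix 2 single-lesion rule does not clearly cover it.

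**5. SPD nadir.** The size sum in 7.1.1.5 takes measurable lesions only. Nothing says whether the earlier size of a lesion that later becomes measurable enters the nadir. Take two lesions on spiral CT, 12x12 and 9x9 mm, where the second grows to 10x10 mm.

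- Measurable lesions only: 144 to 144 + 100 = 244, which is +69%.
- Both lesions throughout: 144 + 81 = 225 to 244, which is +8%.

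The 50% limit is crossed or not according to a rule that is not stated.

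**6. Number affected.** This would need the share of subjects with a baseline plasmacytoma, the share of those below the limit, and the share scanned by standard CT. The documents give none of these.

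**The case against.** The strongest reply is that 7.1.1.5 is a measurement section and defines neither endpoint. The analysed status comes from one algorithm under one set of criteria. Until the primary analysis, the Sponsor's Medical Reviewer also checked each reported PD against IMWG (Section 7.1.1). The scans needed to show that a lesion has gone are already required, and Section 7.1.1.5 and Table 7.1 add a clinical examination on Day 1 of every cycle. The single-lesion PD example needs standard CT.

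Most of this stands, and it rules out three stronger readings.

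- *PFS and CR have two competing definitions.* They do not; each is defined once, through the modified IMWG criteria.
- *Becoming measurable is itself PD.* The text says when a small lesion enters the progression assessment, not that crossing the limit is an event. A lesion going from 19x19 to 20x20 mm (+5% diameter, +11% area) need not be PD under either text.
- *A countable number of events is at risk.* If one assumed that 5–15% of 302 subjects have a plasmacytoma (15–45) and that a third of those are below the limit, 5–15 subjects would result. Neither share comes from the documents. Treating all of them as changed PFS or CR calls would also require every outcome to flip. A changed PFS date needs growth in the gap between the rules to be the first sign of progression. A changed CR needs negative immunofixation and under 5% marrow plasma cells while a small lesion persists.

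The reply does not remove the CR problem. The Sponsor's check covers reported PD, not CR, and an algorithm cannot use lesions that sites were told not to follow.

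**Conclusion.** The point holds as an inconsistency in lesion-level data rules. For CR it follows from the wording alone: 7.1.1.5 does not follow small baseline lesions for response, while Appendix 2 accepts none remaining. For PFS it is narrower. The single-lesion mismatch arises on standard CT when a lesion's short axis was above 1 cm and at least one of its diameters is still below 20 mm after growth of 50% or more; on spiral CT or MRI it largely disappears. The unstated SPD nadir can matter with either technique.

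The effect on the CR rate or on PFS cannot be computed from the documents. It is probably small, because it needs a sub-threshold plasmacytoma whose status decides the call. No sample-size figure changes. The conclusion assumes that sites recorded lesions as 7.1.1.5 directs; if the case report form captured every baseline plasmacytoma whatever its size, the practical effect could be nil, and a short report would show that.

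**What to change.** Reconcile 7.1.1.5 with Appendix 2, which already governs the analysed endpoints, and carry the same wording into the algorithm specification:

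1. Every baseline plasmacytoma, measurable or not, is recorded as present or absent on the scans already required, and must be absent for a derived CR.
2. The 20 mm and 10 mm limits apply only to the size calculation for partial and minimal response.
3. A small lesion entering the progression assessment is assessed by the Appendix 2 PD criteria, with its earlier size included in the SPD nadir. State also how a single lesion whose earlier short axis was 1 cm or less is handled, since Appendix 2 does not clearly cover it.

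The primary cutoff (21 July 2020, Table 7.3) has passed, so new wording cannot repair data already collected. Also report, by arm, how many subjects had a baseline plasmacytoma below the limit, the imaging technique used, and whether any CR or PFS call changes under these rules.

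The cost is wording, a check of the algorithm, and a look back at existing lesion records or local scan reports. No extra scans are needed. The downside is that a few CRs may be downgraded.
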